6. STATISTICAL CONSIDERATIONS

9.1 General Design Issues

Cross over design is the most appropriate to compare one intervention in the same groups of persons

Length of washout chosen is 30 to 60 minutes because after this period, following parameters are stabilized after intervention (PaO₂, PaCO₂, pH)

9.2 Outcomes

Discuss how the outcomes will be analyzed. Describe whether the documentation of an outcome will be reviewed and adjudicated by a committee, how quickly the committee will perform the adjudication, and whether the committee will be masked

to the participant's intervention group assignment.

Primary Outcome

PaO₂ is the primary outcomes observed. PaO₂ is the principal parameters observed

Secondary Outcomes

PaCO₂, pH, MRC dyspnea and comfort

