1.2 Secondary Objectives

The Secondary objectives is the change of PaCO2, pH and patient respiratory comfort with the mask addition above prongs

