4. SELECTION AND ENROLLMENT OF PARTICIPANTS

4.1 Inclusion Criteria

- *At least 18 years of age*
- *Diagnosed with severe Hypoxia (PaO₂/FiO₂ < 300 mm Hg)*
- *Dyspnea with severe rest at stake accessory muscles of respiration*
- *Respiratory rate (RR) ≥ 25 CPM*
- *PaCO₂ ≤ 45 mmHg, patient with an arterial catheter and without hemodynamic instability*
- *Glasgow Coma Scale ≥ 12/15*
- *Written consent.*
- *Participants were also required to have a sufficient level of education to understand study procedures and be able to communicate with site personnel.*

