5. STUDY INTERVENTIONS

Interventions, Administration, and Duration

Sequence (Figure 1): The patient should be placed in semi-seated (position at 45 °) Patient will be oxygenated with high-flow nasal cannula (HFNC). Fraction delivered in Oxygen and flow rate will be adjusted to obtain a Saturation in oxygen > at 90%.

- 1. Arterial gazometry will be taken after 20 and 60 minutes with HFNC.*
- 2. The clinician will associate the Double Trunk Mask (DTM) with the same parameters of the high-flow nasal cannula. Arterial gazometry will be performed after 20 and 60 minutes after placement of DTM.*
- 3. After the withdrawal of DTM, arterial gazometry will be performed after 20 and 60 minutes*

Consenting Procedure

The protocol and informed consent documents were reviewed and approved by a recognized ethics review board at the study facility. The study was performed in accordance with the Declaration of Helsinki.

Enrollment, Baseline, and/or Randomization

Enrollment

Enrolled participants had severe hypoxia being treated at Intensive Care Unit associated with a hospital in Hornu (Epicura).and Tivoli Hospital.

Baseline Assessments

For participants who have successfully been screened for eligibility and are enrolled into the study, baseline assessments are performed against which to measure the study outcome:

Age, Weight, Height, arterial pressure (S/D/M), Cardiac frequency, respiratory frequency, PaO₂, PaCO₂, pH, MRC dyspnea, MRC Comfort, Glasgow Coma Scale.

Blinding

Data's should be evaluated in blind by an independent assessor

Adverse Event Assessment

Safety was assessed by the number of participants with adverse events (AEs). AEs were collected by systematic assessment using terms from the Medical Dictionary for Regulatory Activities (MedDRA), version 11.1 in participants who received one or more doses of intervention. Adverse events during washout were not collected.

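### The dyspnea secondary outcome names an undefined MRC scale; if this is the standard activity-graded one, it is unlikely to detect change between conditions about an hour apart, and a null result would be uninformative

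*Combined protocol and SAP*

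**What the plan says.** Section 9.2 gives the secondary outcomes as PaCO2, pH and "MRC dyspnea and comfort". Under Baseline Assessments, section 5 lists "MRC dyspnea, MRC Comfort, Glasgow Coma Scale" and explains that "baseline assessments are performed against which to measure the study outcome". The ratings are therefore meant to show within-patient change as well as to describe the patients at entry.

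The Précis and section 1.2 are narrower. They name PaCO2, pH and "patient respiratory comfort with the mask addition above prongs", and do not mention dyspnea.

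For neither scale do the documents give grades, item wording, score range, recall period, source or assessment time. The 20- and 60-minute points in the Précis and section 5 are stated for arterial gases only. On posture, section 5 says "The patient should be placed in semi-seated (position at 45" degrees). Among the entry criteria in section 4.1 are a respiratory rate of at least 25 and "Dyspnea with severe rest at stake accessory muscles of respiration". The wording of that last criterion is garbled but appears to mean dyspnea at rest.

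**The concern.** MRC dyspnea is the name of a standard instrument that grades breathlessness by the level of activity that brings it on. It does not ask how breathless the patient feels at this moment. The trial compares high-flow oxygen with and without the mask, within the same patient, over short periods at rest. An instrument tied to activity is a poor match for that question.

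The risk is one of interpretation. An unchanged MRC grade could be reported as showing that the mask does not affect dyspnea, when the scale had little chance of showing an effect in either direction. How the patient feels with a mask added over the prongs is part of what the trial sets out to learn, since respiratory comfort is a stated secondary objective. Two hospitals are listed as sites, so an undefined scale could also be scored differently from one to the other.

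**Working it through.** **The plan's own figure.** There is none for dyspnea or comfort. The only sample-size figure, in section 9.3, is 15 participants for 90% power to detect 10 mm Hg in PaO2 at two-sided 0.05. No standard deviation is given, so it cannot be reproduced, and it does not bear on this point. The number 15 is used below only as the planned sample size.

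**How far apart the ratings would be.** In the section 5 sequence, the sample 60 minutes into high-flow oxygen alone and the sample 60 minutes after mask placement are 60 minutes apart if one step follows directly on the other. Section 3 gives a washout of 20 minutes and section 9.1 gives 30 to 60 minutes. The longest of these would make the gap 60 + 60 = 120 minutes. This assumes that the ratings would be taken with the gases, which the documents do not say.

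**What an activity-graded scale would do in that interval.** There are two ways to answer it, and they are alternatives that should not be added together.

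- If the patient answers about usual activity, the grade describes status before the session and has no reason to differ between conditions.
- If the patient answers about the present state, the entry criteria select people who appear breathless at rest. They would tend to sit near the worst grade, leaving little room for worsening to register. Improvement could still register.

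Either way the scale is insensitive. Only the first reading, applied strictly, gives no movement at all.

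**How insensitive, if some patients do change grade.** Section 9.3 names repeated-measures ANOVA and no separate method for an ordinal grade, so an exact sign test is used here as a simple yardstick. It assumes that every patient who changes grade improves.

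- Two-sided p when k patients change, all in one direction: p = 2 × 0.5^k.
- k = 5: 2 × 0.03125 = 0.0625.
- k = 6: 2 × 0.015625 = 0.031.
- So at least 6 of 15 patients must change grade.

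The chance of reaching 6 or more is P(X ≥ 6), with X binomial (15, q), where q is the assumed true share improving by at least one grade:

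| q | P(X ≥ 6) |
|---|---|
| 0% | 0 |
| 10% | 0.002 |
| 20% | 0.06 |
| 30% | 0.28 |
| 40% | 0.60 |
| 50% | 0.85 |

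The shares are assumptions; the documents give nothing from which to estimate them. Power is exactly zero only at q = 0. It stays below 0.3 up to q = 30%.

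**The case against.** The strongest objection is that the documents never say the scale grades everyday activity. That content comes from general knowledge of the instrument, and the baseline list weakens the inference. It places an MRC Comfort item beside MRC dyspnea, and an activity grading cannot measure comfort, so MRC may be a loose label for a local or adapted rating of how the patient feels now. Taking the baseline value as the reference for the outcome also suggests that the team expected the ratings to move.

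Much of this stands. The conclusion has to be conditional on the standard scale being meant, and it is weaker for comfort. Section 9.2 can be read as MRC dyspnea plus a separate comfort rating, and nothing shows that comfort cannot be measured.

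A reader might go further and infer that the dyspnea score cannot change, so that the mask-minus-no-mask difference is zero by construction. The documents do not support that. Patients or staff may re-rate an ill-fitting scale, perhaps spuriously, and the table above shows appreciable power if 40% to 50% of patients changed grade in one direction. Nor can it be said that everyone enters at the worst grade. That rests on a garbled criterion, and it conflicts with reading the scale as a record of status before admission.

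The objection does not remove the point. Knowing what a named scale measures is ordinary methodological knowledge, and the documents offer no other definition. If something else is meant, the plan does not say what, and the same amendment is needed.

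**Conclusion.** The concern holds in conditional form. The dyspnea and comfort instruments and their assessment times are undefined. If MRC dyspnea is the standard activity-graded scale, it is unlikely to detect change between conditions about an hour apart in patients kept semi-seated, and a null result should not be read as no effect. On the sign-test illustration, the chance of a significant result with 15 patients is about 0.06 to 0.28 when 20% to 30% truly improve.

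This rests on three assumptions: the standard scale is meant, the ratings would be taken near the gas samples, and patients keep the 45-degree position throughout. For comfort, the defect is an unexplained label on a stated secondary objective. PaO2, PaCO2 and pH are untouched. The point therefore merits an amendment but does not threaten the primary comparison.

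**What to change.** In section 9.2 and in Baseline Assessments (section 5), replace the two MRC items as outcomes with two patient-rated 0-10 numeric scales:

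- *breathlessness right now* (0 none, 10 worst imaginable);
- *respiratory comfort right now* (0 worst, 10 best).

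Ask both just before each existing 20- and 60-minute arterial sample in every phase. Keep MRC dyspnea only as a baseline descriptor of prior status, and add dyspnea to section 1.2 if it is to remain an outcome. If the sponsor means a different MRC instrument, give its source, grades, recall period and assessment times, and confirm that it can be scored for breathlessness at rest.

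The cost is small. The three-step sequence in section 5 has 3 × 2 = 6 sampling times, so at most 6 × 2 = 12 ratings per patient plus baseline, each taking seconds at a bedside visit already made for the gas. Self-rating looks feasible, because section 4.1 requires patients to be able to communicate with staff and section 4.2 excludes acute confusion. The downsides are a few CRF lines and no MRC-based outcome to report. Patients will know whether the mask is on, as they would with any self-rated scale.

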9.3 Data Analyses

All participants who received this intervention and completed two phases of study were included in the efficacy analysis.

A sample size of 15 participants was needed to provide 90% power to detect a 10 mm Hg difference in PaO₂. ANOVA for repeated measures followed by a post hoc test were used to compare the difference between participants receiving (high-flow nasal cannula + DTM) and with high-flow nasal cannula alone.

The test was performed with a significance level of 0.05 (two-sided). Statistical analyses were carried out using SigmaPlot software version 11.0 (Systat Software Inc. UK).

Note: In accordance with NIH policy, if data from prior studies do not negate strongly the existence of significant differences of clinical or public health importance in the intervention effect between gender and racial/ethnic subgroups, a statement should be included noting that a valid analysis of the intervention effect will be performed in these subgroups. If data from prior studies do not strongly support the existence of significant differences in the intervention effect between subgroups, then the analyses need not have high statistical power for detecting clinically meaningful differences.

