3. STUDY DESIGN

This is a single-center, randomized, blind investigator, 2-way crossover study design. Enrolled participants had severe hypoxia being treated at Intensive Care Unit associated with a hospital in Hornu (Epicura) and hospital Tivoli.

The study consisted of two intervention periods separated by a washout period of 20 minutes. (Figure 1)

The objective of the study is to determine whether adjunctive mask of our design (Double Trunk Mask - DTM) has an effect on increasing arterial pressure in Oxygen (PaO2) diagnosed with severe hypoxia (See figure 1).

The protocol and informed consent documents were reviewed and approved by a recognized ethics review board at the study facility. The study was performed in accordance with the Declaration of Helsinki.

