4.2 Exclusion Criteria

- *Hypercapnia (> 45 mm Hg with respiratory acidosis)*
- *Cardiogenic pulmonary edema*
- *COPD*
- *Pulmonary fibrosis*
- *Hypoventilation obesity syndrome*
- *Arterial pressure < 60 mm Hg or treatment by epinephrine > to 0,1 gamma/kg/minute*
- *Deterioration of awareness (Glasgow scale < or = 12)*
- *Acute confusional state.*

Participants were randomized in a 1:1 ratio to receive either (CHFONP) classical High Flow Oxygenation with nasal prongs (20 minutes) or CHFNOP with an adjunctive of a DTM.

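### The declared design randomises the order of HFNC and HFNC + DTM, but section 9.3 names no period or sequence term, so a PaO2 shift between periods goes into the error and costs power.

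*Combined protocol and SAP*

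**What the plan says.** Section 3 states: "This is a single-center, randomized, blind investigator, 2-way crossover study design". It adds: "The study consisted of two intervention periods separated by a washout period of 20 minutes". The allocation sentence stands at the end of section 4.2: "Participants were randomized in a 1:1 ratio to receive either (CHFONP) classical High Flow Oxygenation with nasal prongs" or the same with the DTM added. Every patient in a crossover receives both conditions, so what such an allocation randomises is the order.

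Section 5, like the Interventions and Duration part of the Précis, describes a single order for every patient: HFNC, then DTM added, then DTM removed. Its last step reads: "After the withdrawal of DTM, arterial gazometry will be performed after 20 and 60 minutes".

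Section 9.3 holds the whole analysis plan: "ANOVA for repeated measures followed by a post hoc test were used to compare the difference between participants receiving" HFNC + DTM with HFNC alone. It also says "A sample size of 15 participants was needed to provide 90% power to detect a 10 mm Hg difference in PaO₂" and sets a two-sided 0.05 level. It lists no model factors. Neither period, sequence nor carryover is named as a term anywhere, and no SD is given.

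**The concern.** In a two-period crossover with randomised order, the standard model separates the treatment effect from any change between the first and second period. If PaO2 moves by p mm Hg from period 1 to period 2, the DTM-minus-HFNC difference is the mask effect plus p in patients who start on HFNC, and the mask effect minus p in those who start with the DTM. A comparison that looks only at mask against no mask treats this systematic spread as random error.

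Also, 15 patients cannot divide equally, so a fraction of p stays in the mask estimate. At stake is whether the trial has the 90% power it claims and whether its confidence interval has the right width. The problem arises even with one blood gas per period, so it is separate from how the 20- and 60-minute gases are handled.

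**Working it through.** **Inputs from section 9.3.** N = 15, difference 10 mm Hg, power 90%, two-sided alpha 0.05.

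**Assumptions, because the documents give no figure.** SD of the within-patient difference; shift p of 0 to 15 mm Hg; one gas per period; no carryover; analysis as a paired comparison with 14 df.

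**1. The plan's own figure.** Without an SD, N = 15 cannot be reproduced. Solving the noncentral paired t for 90% power at n = 15 gives an SD of 11.1 mm Hg (11.9 by the normal approximation). I use 11.1.

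**2. Leak into the estimate.** With n1 patients HFNC-first and n2 DTM-first, the unadjusted mean difference is off by p × (n1 − n2)/15.
- 8:7: p/15, which is 0.33, 0.67 and 1.00 mm Hg for p = 5, 10 and 15.
- 10:5: 5/15 of p, or 3.3 mm Hg for p = 10.
- 11:4: 7/15 of p, or 4.7 mm Hg for p = 10.

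**3. Inflated error at 8:7.** SD = √(11.1² + p² × (1 − 1/225) × 15/14).
- p = 5: √(123.2 + 26.7) = 12.2
- p = 10: √(123.2 + 106.7) = 15.2, which is 1.37 times 11.1
- p = 15: √(123.2 + 240.0) = 19.1

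**4. Power at 8:7 by simulation, true effect 10 mm Hg.** The two unadjusted columns differ in whether the extra patient is in the order that makes the shift favour the mask.

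| Shift (mm Hg) | No period term, favourable | No period term, unfavourable | With period term |
|---|---|---|---|
| 0 | 90% | 90% | about 89.5% |
| 5 | 88% | 83% | about 89.5% |
| 10 | 77% | 63% | about 89.5% |
| 15 | 57% | 33% | about 89.5% |

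The adjusted analysis averages the two sequence means. Its standard error is (11.1/2) × √(1/8 + 1/7) = 2.87 on 13 df, against 11.1/√15 = 2.87 on 14 df unadjusted with no shift. The cost is therefore almost only the degree of freedom: 90.0% to 89.5%.

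**5. Type I error.** At 8:7 the unadjusted test is conservative: about 3.4% at p = 5 and 1.1% at p = 10. Given an unequal split and p = 10, it is about 7% at 10:5 and 16% at 11:4. With the term it is about 5% throughout.

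**6. Simple, unblocked randomisation.** From the binomial (15, 0.5), a 10:5 or worse split has probability 0.302 and an 11:4 or worse split 0.118. Averaged over all splits, unadjusted type I error is about 5% and the estimate is unbiased. Unadjusted power is 84%, 67% and 47% at p = 5, 10 and 15, against about 87% with the term.

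**7. If every patient follows HFNC then DTM.** The shift adds in full to the mask effect in the two-phase comparison. With p = 10 and no mask effect, the test would reject about 90% of the time, and no period term could be fitted to separate the two.

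**The case against.** The strongest reply is that randomised order is inferred. The allocation sentence in section 4.2 does not mention order, and section 5 sets out one sequence for all. A repeated-measures ANOVA with a post hoc test also fits that three-phase schedule. This stands as a condition on the remedy: with one order there is nothing to adjust for. It does not rescue the analysis, because a fixed order confounds period with mask in the two-phase comparison.

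Second, section 9.3 is silent on model terms. A reader might infer that a treatment-only model was deliberately chosen; the text shows only that none of the needed terms is specified. Followed as written, however, it compares mask with no mask and nothing else.

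Third, no shift is documented, and shifts of 10 and 15 mm Hg equal or exceed the target effect. At 5 mm Hg and 8:7 the loss is modest, 2 to 7 points. A reader might take section 9.1, with its 30 to 60 minutes for gases to stabilise, as evidence of a shift. It is not: that sentence concerns recovery after the intervention, which bears on carryover. What remains is that patients are acutely ill (section 4.1: respiratory rate of at least 25, dyspnoea), so a drift is plausible but of unknown size.

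Fourth, a reader might infer that the omission inflates false positives in general. It does not: the test is conservative at 8:7, and its overall type I error under simple randomisation is about 5%.

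**Conclusion.** The point holds in this form: under the declared randomised crossover, section 9.3 omits the period and sequence terms, and any shift between periods is paid for in power. At 8:7, power falls from 90% to 83-88%, 63-77% or 33-57% for shifts of 5, 10 or 15 mm Hg; under simple randomisation it is 84%, 67% or 47%. The leak into the mask estimate at 8:7 is only 1/15 of the shift. Larger bias, and the false-positive rate of about 16% at 11:4 with a 10 mm Hg shift, arise only conditional on an unequal split. The documents say nothing about blocking, and the restriction to completers in section 9.3 could also unbalance the split.

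The algebra does not depend on the SD. The percentages do: they rest on the back-solved 11.1 mm Hg, an assumed shift, one gas per period and no carryover.

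**What to change.** 1. Reconcile the single order in section 5 and the Précis with the randomised two-way crossover in sections 3 and 4.2. The next steps apply only if order is randomised.
2. In section 9.3, analyse PaO2, PaCO2 and pH with patient as a random effect and treatment, period and sequence as fixed effects. Equivalently, regress each patient's DTM-minus-HFNC difference on order coded +1/−1 and test the intercept. Report the period-adjusted mean difference with its 95% CI.
3. In the allocation sentence of section 4.2, state that order comes from a permuted-block list, so that the split stays near 8:7.

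The cost is a few sentences, a blocked list and one degree of freedom, with no extra patients or samples. If there is no shift, the term costs about 0.5 point of power at 8:7. It costs more with an unequal split: at 11:4 the adjusted standard error is (11.1/2) × √(1/11 + 1/4) = 3.24 instead of 2.87, which is a further reason to block.

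### The primary ANOVA has no stated error term, period term or time point; one permitted reading gives a true error of about 8–18% (8–21% with four gases) instead of 5%, and a per-patient DTM-minus-HFNC difference avoids this

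*Combined protocol and SAP*

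**What the plan says.** Section 9.3 (Data Analyses) describes the efficacy test as follows: "ANOVA for repeated measures followed by a post hoc test were used to compare the difference between participants receiving" HFNC plus the double trunk mask (DTM) and HFNC alone. The level is two-sided 0.05. The section does not name the factors of the ANOVA, the error term for the DTM effect, the post hoc test, any handling of sphericity, or a period effect. Section 9.2 makes PaO₂ the primary outcome without a time point or a summary over gases.

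The sampling schedule in section 5 (and in the Précis, under Interventions and Duration) has three steps:
- Step 1: "Arterial gazometry will be taken after 20 and 60 minutes with HFNC".
- Step 2: "Arterial gazometry will be performed after 20 and 60 minutes after placement of DTM".
- Step 3: "After the withdrawal of DTM, arterial gazometry will be performed after 20 and 60 minutes".

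That is six gases per patient in a fixed HFNC–DTM–HFNC order. Section 3 describes something else: "The study consisted of two intervention periods separated by a washout period of 20 minutes". Section 4.2 adds 1:1 randomisation between HFNC and HFNC with DTM. Section 9.1 justifies the design this way: "Cross over design is the most appropriate to compare one intervention in the same groups of persons". On the sample size, section 9.3 states: "A sample size of 15 participants was needed to provide 90% power to detect a 10 mm Hg difference in PaO₂".

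**The concern.** Two gases taken 40 minutes apart under the same condition will normally resemble each other more than gases taken under different conditions. A one-way repeated-measures ANOVA over all gases assumes that every pairwise difference has the same variance (sphericity) and pools all residual variation into one error. A DTM-minus-HFNC comparison of phase means depends on variation between phases. The pooled residual also contains the smaller variation within phases, so it is too small for that comparison.

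If the analysis were run this way, the p-value for the primary comparison, and any interval built on the same error, would claim more precision than 15 patients provide. A second gap is that a randomised crossover is analysed with no period term, which can cost power if PaO₂ shifts between periods. Because the sentence does not fix the model, these choices could be made after the data are seen.

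**Working it through.** **1. The plan's own figure.** Inputs from section 9.3: n = 15, 90% power, difference 10 mm Hg, two-sided 0.05. No SD is given, so the figure cannot be reproduced directly. Solving the paired t-test for the SD of the within-patient difference gives 11.1 mm Hg. The normal approximation gives 10√15/(1.960 + 1.282) = 11.9. An SD of 10 would need 13 patients, 12 would need 18, and 15 would need 26.

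**2. Model for the error rate.** Gas value = patient + patient-by-phase + gas error, with no treatment effect. Within-patient variance is set to 1, and ρ is the share of it that is common to a phase. ρ is an assumption; I use 0.2–0.8. Layouts: 3 phases × 2 gases (section 5) and 2 periods × 2 gases (section 3, if both times are used).

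**3. Size of the mismatch.** A phase mean has variance (1 + ρ)/2, but the pooled analysis uses residual/2. The expected residual is 1 minus the average covariance between two gases of a patient:
- six gases: 3 of 15 pairs share a phase, so 1 − ρ/5, on 14 × 5 = 70 df (critical t 1.99)
- four gases: 2 of 6 pairs, so 1 − ρ/3, on 14 × 3 = 42 df (critical t 2.02)

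Ratio of correct to pooled standard error:
- six gases: √(1.2/0.96) = 1.12 at ρ = 0.2; √(1.8/0.84) = 1.46 at ρ = 0.8
- four gases: √(1.2/0.933) = 1.13; √(1.8/0.733) = 1.57

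Dividing the critical value by the ratio (six gases: 1.99/1.12 = 1.78 and 1.99/1.46 = 1.36) gives tail areas of about 8% and 18%.

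**4. Simulation.** 40,000 null trials per setting, n = 15. True two-sided error in %, at ρ = 0.2 / 0.5 / 0.8:

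| Reading of the sentence in 9.3 | Six gases | Four gases |
|---|---|---|
| One-way ANOVA, pooled residual, unadjusted phase contrast | 8.0 / 12.8 / 17.8 | 8.3 / 14.0 / 21.2 |
| Same contrast, only after a significant overall F | 2.3 / 4.1 / 6.0 | 3.3 / 6.0 / 9.0 |
| One 60-minute pair, unadjusted | 5.5 / 6.3 / 7.4 | 6.0 / 7.4 / 9.8 |
| Any DTM–HFNC gas pair, Tukey | 3.5 / 4.1 / 4.1 | 4.4 / 5.6 / 6.2 |
| Overall F | 5.3 / 6.6 / 9.1 | 5.3 / 6.6 / 9.0 |
| Two-way ANOVA, phase contrast against patient × phase error | 5.0 / 5.1 / 4.9 | 4.9 / 5.1 / 4.9 |
| Per-patient contrast, one-sample t | 5.1 / 4.9 / 4.9 | 4.9 / 5.1 / 4.9 |

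At ρ = 0 the first row is 4.8 and 5.0. A single pair under Bonferroni over all pairs is far below 5% by design (0.4–0.7% with six gases) and is left out of the range quoted.

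**5. A different correlation pattern.** Let correlation decay as r^lag over the six gases in order, with contrast weights (−1, −1, 2, 2, −1, −1). The variance ratio is [1 + (2r − 8r² − 3r³ + 2r⁴ + r⁵)/6] / [1 − (5r + 4r² + 3r³ + 2r⁴ + r⁵)/15]. At r = 0.5 this is 0.797/0.731 = 1.09 (true error about 6%). At r = 0.9 it is 0.173/0.211 = 0.82 (about 3%, conservative). Smooth drift can therefore reverse the direction.

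**6. Period term, two-sequence design.** Assume SD 11.1, 8 and 7 patients per sequence, true effect 10 and a period difference of 10 mm Hg. Without a period term the expected variance is 11.1² + 10²(15 − 1/15)/14 = 229.9, an SD of 15.2. The mean difference must then exceed about 2.145 × 15.2/√15 = 8.4. Its expectation is 10 + 10/15 = 10.7 if the larger sequence has DTM in the favourable period, otherwise 9.3. Its true standard error is 11.1/√15 = 2.87. Power is about 78% in the first case (z ≈ 0.8) and about 63% in the second (z ≈ 0.3). The period-adjusted test keeps about 90%. With no period effect the adjustment costs about half a percentage point.

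**The case against.** A reader might infer that the plan does use one pooled error and that its 5% test therefore runs at 8–18%. The documents do not support that. Section 9.3 names no error term or contrast, and a two-way repeated-measures ANOVA that tests condition against patient × condition fits the same words and holds 5%. Section 3 speaks of two periods, section 9.3 of completing two phases, and section 4.2 puts classical HFNC at 20 minutes. One gas per period is therefore a fair reading, and with two periods the ANOVA is then simply a paired t-test. The plan also places a post hoc test after the ANOVA. The gated and Tukey readings with six gases stay between 2.3% and 6.0%. No correlation is documented, and step 5 shows that even the direction depends on it.

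All of this stands, and it limits the claim to a conditional one. It does not close the gap. The same sentence permits tests whose true error ranges from about 2% to about 21%, and nothing in the plan selects among them. The absence of a period term is independent of how the gases are pooled.

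A further fair objection is that a between-sequence crossover t-test cannot be run under a single fixed three-step order. That is correct, so the remedy has to depend on which design is confirmed.

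**Conclusion.** The concern holds in conditional form. The model, error term, post hoc test, period term and primary time point are unspecified, so the stated 0.05 level is not secured. If both gases per phase enter a one-way ANOVA and the unadjusted phase contrast uses the pooled residual, the true error is about 8–18% with six gases and 8–21% with four, for an assumed phase-level share of 0.2–0.8. The other readings examined give about 2–10%. One gas per phase, or a patient × condition error, removes this problem. The figures rest on n = 15, the variance model in step 2 and an assumed ρ. They do not show that the trial's test is inflated, only that the plan does not prevent it. A per-patient contrast held about 5% in every layout checked.

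**What to change.** First reconcile the two-period randomised crossover (sections 3 and 4.2) with the three-step sequence (Précis and section 5). The choice determines how many gases there are and which test can be run.

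Then replace the primary test with one DTM-minus-HFNC PaO₂ difference per patient at a prespecified time:
- **If two sequences (AB/BA):** the period-adjusted crossover t-test (13 df with n = 15), or a mixed model with patient, period and treatment.
- **If the three-step order is kept:** a one-sample t-test on each patient's DTM value minus the mean of the two HFNC phases (14 df). Averaging the bracketing phases cancels linear drift, but not other time trends.

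Keep any multi-gas ANOVA as supportive only, with a Greenhouse–Geisser correction and contrast-specific errors.

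The cost is SAP wording and fewer error degrees of freedom: 70 to 14 or 13, with critical t rising from 1.99 to 2.14 or 2.16. For phase means with six gases, intervals become 1.12 × 2.14/1.99 = 1.20 to 1.46 × 2.16/1.99 = 1.59 times the pooled ones. That is about 20–60% wider at shares of 0.2–0.8; with four gases the upper end is 1.57 × 2.16/2.02 = 1.68. This is the correct width. Using one gas instead of the mean of two raises the standard error by a further √(2/(1 + ρ)), which is 1.29 at ρ = 0.2 and 1.05 at 0.8. If that matters, a per-patient phase mean fixed in advance is equally valid.
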